Radiographic imaging of the dentoalveolar complex has been assessed using conventional periapical radiography, the benchmark for intraoral radiographic imaging for decades. Their known limitations of image magnification, distortion, superimposition and overlap of anatomy always led to unclear and misrepresentation of structures. Although the advent of digital intraoral radiography didn’t improve these limitations, it provided a more active image manipulation than the film-based radiographs and reduced patient exposure substantially. [19, 20]

7 - Objectives and hypothesis:

The objective of this prospective randomized clinical trial is to compare the clinical and radiographic outcomes of MTA and Biodentine as vital pulp therapy materials (pulpotomy) preserving the vitality of traumatized immature anterior permanent teeth.

8-Trial Design:

Randomized clinical trial (RCT), parallel groups with 1:1 allocation ratio, Triple blinded (patient, clinical and radiographic assessor of the results and statistician)

III- Methods:

9-Study settings:

This study will be carried out on patients attending the outpatient clinic in Pediatric Dentistry department, Faculty of Dentistry, Cairo University, Egypt. the procedures will be carried out by [name] Associate Professor of Pediatric Dentistry in Pediatric Dentistry clinic. expected time duration from 2017 to 2018.

10- Eligibility criteria:

Inclusion criteria

- The patient age range 7.5-9 years.
- Noncontributory medical history
- Unilateral/ and or bilateral central incisors tooth with complicated trauma (exposure size $\geq 1\text{mm}$)
- The tooth should give positive response to cold testing
- Clinical diagnosis of reversible pulpitis without periapical rarefaction
- The tooth is restorable, mobility was within normal limits
- No signs of pulpal necrosis including sinus tract or swelling

Exclusion criteria

- Teeth with mature roots
- Signs and symptoms of irreversible pulpitis
- Non-restorable teeth
- Negative response to cold testing, the presence of sinus tract or swelling
- No pulp exposure
- Bleeding could not be controlled after full pulpotomy in 6 minutes

IV- Intervention:

Diagnosis:

1. Full history data will be collected, including personal, medical and previous dental data
2. Clinical examination using mirror and probe to assess the inclusion criteria.
3. Radiographic examination using preoperative digital periapical radiograph to assess the inclusion criteria.

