Secondary outcome	Stage of root development	Standardized periapical	4 stages
	Presence of radiolucency	Standardized periapical	Binary

Primary outcome:

Clinical assessment of the findings in the table will be conducted at follow up intervals (baseline, 6, 12 and 18 months)

Secondary outcome:

Radiographic assessment of stage of root development, and presence of radiolucency will be conducted through digital periapical radiographs by parallel technique using film holders. The assessments will be carried out at follow up intervals (baseline, 6, 12 and 18 months)

13- Participants timeline:

	Study period				
	Enrolment	Allocation	Post allocation		Close out
Time point	For 9 months	0	6 months	12 months	18 months
Enrolment:					
Eligibility screen	✓				
Informed consent	✓				
History taking	✓				
Clinical examination	✓				
Preoperative radiograph	✓				
Allocation		✓			
Interventions:					
Access preparation		✓			
Placement of Biodentine (experimental group)		✓			
Placement of MTA (Control group)		✓			
Final restoration		✓			
Assessment					
Periapical radiograph as baseline reference			✓	✓	✓
Clinical examination to assess pain, swelling, fistula, tooth mobility			✓	✓	✓
Periapical radiograph to assess stage of root development and presence of radiolucency			✓	✓	✓

14- Sample size calculation:

Sample size is calculated based upon the results of Alqaderi et al (2014) [21] who reported clinical success rate (primary outcome) for MTA = 90%. Since no relevant literature reported the clinical success rate of Biodentine in permanent teeth of pediatric patients, the success rate was assumed to be 50%. Using alpha level = 0.05 and β level = 0.20 (80% Power); the minimum estimated sample size will be 20 subjects per group for a total of 40 subjects. To compensate for a drop-out rate of 15%, the number is increased to 23 subjects per group for a total of 46 subjects.

Sample size calculation will be performed using IBM® SPSS® Sample Power® Release 3.0.1.

15- Recruitment:

All patients attending the outpatient clinic in pediatric dentistry department complaining from traumatized immature permanent maxillary central incisors will be screened and enrolled in the study if they meet the eligibility criteria.

16- Allocation:

Sequence generation:

Access cavity in traumatized central incisors will be assigned into experimental or control group using simple randomization 1:1 by the help of the computer software(random.org).

Allocation concealment mechanism:

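### Enrolling 46 children keeps the stated minimum of 40 for about 13% drop-out, not the stated 15%; the slip is in the allowance and costs almost no power

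*Combined protocol and SAP*

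**What the plan says.** Section 14 (Sample size calculation) takes the MTA success rate from a published study, "who reported clinical success rate (primary outcome) for MTA = 90" per cent. For Biodentine it found no relevant literature, so "the success rate was assumed to be 50" per cent. With alpha 0.05 and 80% power it concludes that "the minimum estimated sample size will be 20 subjects per group for a total of 40 subjects". The next sentence makes the allowance for losses: "To compensate for a drop-out rate of 15%, the number is increased to 23 subjects per group for a total of 46 subjects".

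Section 8 (Trial Design) specifies "parallel groups with 1:1 allocation ratio". Section 14 does not write out the inflation formula, and it does not say whether alpha is one-sided or two-sided. No other section gives a different enrolment target or a further allowance for losses.

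**The concern.** An allowance for drop-out is normally read in one way: if the stated fraction of those enrolled is lost, the stated minimum still remains. Here 46 children less 15% is fewer than 40, so the two sentences of Section 14 do not agree.

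The figure matters because 46 is the trial's only enrolment target and this sentence is its justification. Losses are also a real prospect: children aged 7.5 to 9 years are followed for 18 months, Section 19 plans retention measures, and Section 20 describes no handling of missing outcomes. At stake is whether the trial has the margin that it says it has.

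**Working it through.** **Inputs.** All come from Section 14, except the allocation ratio (Section 8):
- success rates 0.90 (MTA) and 0.50 (Biodentine, assumed), so the difference is 0.40 and the mean is 0.70;
- alpha 0.05, taken as two-sided (my assumption, since the section does not say); power 0.80; allocation 1:1;
- minimum 20 per group (40); drop-out 15%; enrolment 23 per group (46).

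**Step 1: reproduce the minimum.** Pooled normal approximation without continuity correction:

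n per group = [1.960 x √(2 x 0.70 x 0.30) + 0.842 x √(0.90 x 0.10 + 0.50 x 0.50)]² / 0.40²

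= [1.2702 + 0.4907]² / 0.16 = 19.38, rounded up to 20. This matches the protocol.

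**Step 2: reproduce the inflated figure.** 20 x 1.15 = 23.0, which matches exactly.

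**Step 3: what remains after 15% loss.**
- Per group: 23 x 0.85 = 19.55, below 20.
- In total: 46 x 0.85 = 39.1, below 40.

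**Step 4: what loss 46 does cover.** (46 - 40)/46 = 6/46 = 13.0%. Per group it is the same: 3/23 = 13.0%.

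**Step 5: what 15% would need.** 20/0.85 = 23.53, rounded up to 24 per group (48 in total). Starting from the total, 40/0.85 = 47.06, which is again 48 with equal groups. Check: 48 x 0.85 = 40.8.

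**Step 6: effect on power.** With the Step 1 formula solved for power, Φ{[0.40√n - 1.2702] / √0.34}:

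| Completers per group | Power |
|---|---|
| 20 | 81.3% |
| 19.55 (expected at 15% loss from 23) | 80.4% |
| 19 | 79.2% |

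The expected shortfall is 40 - 39.1 = 0.9 of a child, and the power difference from 20 to 19.55 is 0.9 of a percentage point.

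**The case against.** The strongest objection is that 23 per group does meet the design's real target. The formula that gives 20 needs only 19.38 before rounding. A 15% loss from 23 leaves 19.55, which is above 19.38, so 80% power is kept in expectation. Moreover, 19.38/0.85 = 22.80 also rounds up to 23, so the figure could have come from the usual division applied to the unrounded requirement. The shortfall would then be a product of rounding.

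Much of this stands. A reader might infer from the match with 20 x 1.15 that the protocol multiplied where it should have divided. The match is exact, and the text speaks of increasing the stated number, so that reading is plausible. But the formula is not shown, and it cannot be given as fact. What remains does not depend on the mechanism: Section 14 names 20 per group (40) as its minimum, and 46 x 0.85 is below 40 however 46 was reached.

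Rounding in whole children does not rescue the sentence. Fifteen per cent of 23 is 3.45. Losing 3 leaves 20, but 3/23 is a 13.0% loss; losing 4 leaves 19. Over both groups, 15% of 46 is 6.9, and losing 7 leaves 39.

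Two further points limit the importance. Section 16 specifies simple randomization, under which an exact 23/23 split of 46 children has only about a 12% chance, so a difference of one child per group is within the design's own play. Section 20 also plans a log-rank comparison, to which a child lost after a follow-up visit still contributes.

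**Conclusion.** The stated drop-out allowance is wrong on Section 14's own figures, by a small margin: 46 keeps the minimum of 40 for a loss of up to 13.0%, and at 15% about 39 children are expected to complete. Power stays at about 80% (80.4% at 19.55 per group). The arithmetic on completers needs no assumption beyond the printed numbers. The power figures assume 90% against 50% and a two-sided pooled test without continuity correction; a one-sided calculation with continuity correction also gives 20, so the protocol's method is inferred.

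Three stronger readings are not supported.
- **That the trial is underpowered because of this slip.** By the formula that reproduces the protocol's 20, even a whole 19 per group gives 79.2%.
- **That missing 40 completers is a serious failure.** If each child independently has a 15% chance of dropping out, the chance of fewer than 40 completers is 55% with 46 enrolled. That is what an expected value near 40 produces; 48 enrolled still leaves 29%.
- **That the loss is large under Fisher's exact test.** Section 20 names chi-square and Fisher's tests without saying when each applies. With Fisher's test throughout, exact power is already 74.2% at 20 per group with no shortfall, so most of the gap from 80% comes from the choice of test. With 39 completers split 19 and 20, it is 75.9% or 79.7%, depending on which group is smaller.

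**What to change.** Replace the drop-out sentence in Section 14, leaving enrolment at 46, with text such as:

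> Enrolling 23 per group (46) keeps the minimum of 40 for a drop-out of up to 13%; at 15%, about 39 children are expected to complete, with about 80% power by the two-sided pooled normal-approximation formula without continuity correction.

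Naming the formula matters, because the power figure belongs to that method. The protocol authors should confirm that it is the one they used, and should state how 23 was obtained.

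The cost is one sentence and a slightly less favourable stated allowance; no child is added and no analysis changes. If the 15% allowance is to be kept against the minimum of 20, the matching figure is 24 per group (48). That means two more children and a change of sample size, for which Section 25 requires a formal amendment.

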Clinical and Radiographic Evaluation of Pulpotomy Technique for Preserving Vitality of Traumatized Anterior Permanent Immature Teeth: A Randomized Clinical Trial

Protocol submitted to the Faculty of Dentistry, Cairo University
by
[name]
Associate Professor of Pediatric Dentistry

Faculty of Dentistry
Cairo University
January 18 , 2017

I. Administrative information:

1. Title:

Clinical and Radiographic Evaluation of Pulpotomy Technique for Preserving Vitality of Traumatized Anterior Permanent Immature Teeth: A Randomized Clinical Trial

2. Protocol Registration:

To be registered on Clinicaltrial.gov

3. Protocol version:

Final version.

4. Funding:

This trial is self-funded.

5. Roles and responsibilities:

1. **[name] ([name])** Associate Professor of Pediatric Dentistry, Cairo University. Responsible for the clinical part of study, and Data monitoring.
2. **[name] ([name])** Professor of Pediatric Dentistry, National University of Singapore, responsible for the writing revision and proof reading.
3. **[name] ([name])** Associate Professor of Pediatric Dentistry, Misr University for sciences and technology. Responsible for the clinical evaluation of the cases at the evaluation intervals

II. Introduction

6-background and rationale:

Description of research question:

P: children with vital traumatized exposed immature maxillary permanent incisors

I: Pulpotomy using Biodentine

C: MTA pulpotomy

O:

	Outcome	Tool/Device	Unit
Primary Outcome	spontaneous pain, sensitivity to percussion/ palpation)	Pain questionnaire	Binary
	Swelling or sinus tract	Visual examination by the third author	Binary
	Mobility	Back of the mirror	Binary
Secondary outcome	Stage of root development	Standardized periapical	4 stages
	Presence of radiolucency	Standardized periapical	Binary

S: Randomized clinical trial

T: 18 months (Baseline, 6, 12 and 18 months)

Research question: is Biodentine used as pulpotomy material in vital traumatized exposed immature maxillary permanent central incisors more successful clinically and radiographically than MTA pulpotomy?

Justification for undertaking the trial:

The occurrence of dental trauma in permanent teeth is a common event worldwide [1]. Children and adolescents are most frequently affected, and two-thirds of all dental trauma are found among these populations [1,2], with the anterior permanent teeth being the most affected [1, 4-6].

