4. Preoperative photograph will be taken.

Operative procedure:

Experimental group:

1. Injection of local anesthesia and rubber dam isolation.
2. Roof of the pulp chamber will be removed by a fissure diamond bur (Diatech, Heerbrug, Switzerland) and high-speed handpiece with coolant.
3. The pulps will be amputated to the orifice level using a long-shank diamond round bur.
4. Haemostasis will be achieved by gentle placement of a saline-moistened cotton pellet over amputated pulps for 5–10 min.
5. Calcium silicate-based Biodentine™ (Septodont Ltd., Saint Maur des Fausse's, France) will be mixed according to the manufacturer's instructions, radicular pulp will be covered by the material using a wet cotton pellet.
6. A self-cure glass ionomer (GC; GC Corporation, Tokyo, Japan) will be placed over the pulpotomy agent before final restoration of composite resin (Clearfil™, Kuraray, New York, USA) will be done.
7. Immediate post-operative radiograph and photograph will be taken.

Control group:

The same procedures will be carried out as the experimental group, but the pulp stumps will be covered with white mineral trioxide aggregate (MTA) ProRoot® MTA (Dentsply/ Johnson City, TN, USA) will be used as the reference material for comparison and will be prepared according to the manufacturer's instructions. A 3-mm-thick layer of MTA will be placed over the amputated pulps and will be gently adapted to the dentinal walls using a wet cotton pellet deep onto the radicular pulp. A self-cure glass ionomer (GC; GC Corporation, Tokyo, Japan) will be placed over the pulpotomy agent before final restoration of composite resin (Clearfil™, Kuraray, New York, USA) will be done.

Postoperative care:

Instructions to avoid lip biting in addition to oral hygiene measures.

Follow up:

Assess the outcomes clinically and radiographically at (baseline, 6, 12 and 18 months).

Criteria for discontinuing or modifying intervention:

In case of an unsuccessful outcome after pulpotomy, the teeth will be managed by other pulp therapy techniques.

Strategies to improve adherence to intervention:

Explanation to the parents about the importance of follow up visits in addition to treatment of other dental problems.

Concomitant care:

None needed.

12- Outcomes:

	Outcome	Tool/Device	Unit
Primary Outcome	spontaneous pain, sensitivity to percussion/ palpation)	Pain questionnaire	Binary
	Swelling or sinus tract	Visual examination by the third author	Binary
	Mobility	Back of the mirror	Binary

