Numbered opaque sealed envelopes.

Implementation:

The child will choose an envelope randomly and open it after access preparation so that the operator knows which pulpotomy agent will be used. Sequence generation will be done by the third author and the patient assignment will be done by the operator.

17- Blinding:

Patients and their parents, the assessor and the statistician will be blinded.

18- Data collection methods:

Primary outcome:

Clinical assessment of the following findings:

1. postoperative pain: through asking the child and the parent if there is pain

either continuous or intermittent

2. Swelling: through visual examination by the assessor either intraorally or extra-orally.
3. Sinus or fistula through visual examination of the gingiva by the assessor.
4. Tooth mobility: By the back of the mirror checked by the assessor to detect mobility in any direction

This assessment will be conducted every follow-up visit throughout the study period at baseline, 6, 12 and 18 months.

Secondary outcome

Radiographic assessment to detect stage of root development and presence of radiolucency through standardized periapical radiograph by parallel technique using film holder. This assessment will be conducted every follow-up visit throughout the study period at baseline, 6, 12 and 18 months.

Postoperative records will be performed by the assessor to avoid individual variability and to promote data quality.

19- Data management:

Explanation to the parents about the importance of the follow-up visits in addition to treatment of other dental problems are plans to promotes participants retention and complete the follow-up.

Also, phone calls before the dates before the next follow-up visit will be scheduled.

All findings will be documented in the examination sheet then transferred electronically to computer in secured lace sequentially.

20- statistical methods:

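### The blinding of the child and the outcome assessor is stated in Sections 8 and 17 but put at risk by the allocation and monitoring procedures in Sections 16 and 21

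*Combined protocol and SAP*

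**What the plan says.** **The stated blinding.** Section 8 (Trial Design) describes the trial as "Triple blinded (patient, clinical and radiographic assessor of the results and statistician". Section 17 (Blinding) adds the parents: "Patients and their parents, the assessor and the statistician will be blinded". Section 17 gives no mechanism.

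**Allocation.** Section 16 uses simple 1:1 randomization and, for concealment, "Numbered opaque sealed envelopes". Under Implementation it says "The child will choose an envelope randomly and open it after access preparation so that the operator knows which pulpotomy agent will be used", followed by "Sequence generation will be done by the third author and the patient assignment will be done by the operator".

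**Who assesses.** Section 5 describes the third-listed investigator as "Responsible for the clinical evaluation of the cases at the evaluation intervals". The outcome table in Section 12 lists swelling or sinus tract as "Visual examination by the third author". Section 18 gives the swelling, sinus and mobility examinations to the assessor and adds "Postoperative records will be performed by the assessor to avoid individual variability and to promote data quality". Pain is obtained by asking the child and the parent.

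**Who monitors.** Section 21 has the assessor regularly monitor study data and results, with full access. Section 29 removes participant-identifying information from data passed to team members and does not mention the arm. Section 5 gives data monitoring to the first-listed investigator, not to the assessor.

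**The concern.** The child and the assessor are declared blind, but each is also given a task through which the arm could be learned. The child handles the allocation document. The assessor writes the sequence and monitors the results.

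These two people, with the parent, supply the primary clinical findings. Section 18 has the assessor make the postoperative records and describes no second rater. Reported pain, and mobility checked with the back of a mirror, leave more room for judgement than visible swelling or a sinus tract. If the arm became known, those findings would be open to detection bias, and the triple-blind description would not be supported by the procedures behind it.

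**Working it through.** **Step 1. Set the sections side by side.**

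| Person | Declared blind | Task that conflicts | Safeguard written |
|---|---|---|---|
| Child | Sections 8, 17 | Opens the envelope that tells the operator the agent (16); later reports pain (18) | None: no coded label, no shielding |
| Parent | Section 17 only | Reports pain with the child (18) | Presence at the opening is not stated |
| Assessor | Sections 8, 17 | Generates the sequence (16) | The child's random draw helps; nothing keeps the opened envelope's number from the list's author |
| Assessor | Sections 8, 17 | Monitors data and results with full access (21) | None: neither 21 nor 29 withholds the arm |
| Statistician | Sections 8, 17 | None found | Not in question |

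That the third author is the assessor follows from reading Sections 5, 12 and 18 together: Section 12 assigns the swelling and sinus examination to the third author, and Section 18 assigns it to the assessor.

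**Step 2. Reproduce the planning figure.** Inputs from Section 14: success 0.90 (MTA) and 0.50 (Biodentine), alpha 0.05 (taken as two-sided), power 80%. With a pooled variance and no continuity correction, the mean rate is 0.70 and

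n = [1.960 × √(2 × 0.70 × 0.30) + 0.842 × √(0.90 × 0.10 + 0.50 × 0.50)]² / 0.40²
= [1.270 + 0.491]² / 0.16 = 3.10 / 0.16 = 19.4, rounded up to 20 per group.

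This matches the protocol.

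**Step 3. How many changed calls move the test?** This shows sensitivity only and does not estimate bias. A changed call means one child reclassified from failure to success in the Biodentine arm. Section 20 names both Fisher's exact test and the chi-square test.

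The expected counts at 20 per group are 18/20 and 10/20. Because the arms are equal in size, the two-sided Fisher p is twice the upper tail.

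- 18 v 10 (28 successes in 40): 2 × [C(20,18)C(20,10) + C(20,19)C(20,9) + C(20,20)C(20,8)] / C(40,28) = 2 × (0.00628 + 0.00060 + 0.00002) = 0.014.
- 18 v 12 (30 successes in 40): 2 × [C(20,18)C(20,12) + C(20,19)C(20,11) + C(20,20)C(20,10)] / C(40,30) = 2 × (0.02824 + 0.00396 + 0.00022) = 0.065.

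| Counts | Calls changed | Fisher p | Chi-square p (uncorrected) |
|---|---|---|---|
| 18/20 v 10/20 | 0 | 0.014 | 0.006 |
| 18/20 v 11/20 | 1 | 0.031 | 0.013 |
| 18/20 v 12/20 | 2 | 0.065 | 0.029 |
| 18/20 v 13/20 | 3 | 0.127 | 0.058 |

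At 23 per group, with counts rounded to 21 and 12, Fisher p is 0.007, and 0.071 after three changed calls. Two or three calls therefore cross the 0.05 threshold, depending on the test and the number analysed. Calls in the other direction would move a result across it the other way.

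**The case against.** The strongest reply is that most of this is silence about safeguards. Section 17 says the assessor will be blinded, and Section 21 can be read subject to that. The envelope may hold a coded label. Because the child draws at random, the list alone does not tell its author any child's arm, and no record linking envelope number to child is described. An assessor also needs access to the records that he or she makes.

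Much of this stands. A reader might infer that the assessor knows the arms, or that the child is told the agent. The documents support neither. No passage gives the assessor the allocation, and what is printed in the envelope is not stated. The sequence-generator overlap is the weakest of the three routes, because it needs the envelope number to reach the assessor. A reader might also take the different data-monitoring roles in Sections 5 and 21 as a sign of lost blinding. They are only passages to reconcile.

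The reply does not remove the point, because these are written procedures and not only gaps. The plan assigns the envelope, the list and the results to people it calls blind, and it writes no restriction on any of the three.

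It could also be said that one call moves a rate by only 1/20 = 5.0 points (1/23 = 4.3) against a planned difference of 40 points. The right yardstick is the planned test, which two or three calls can move across its threshold.

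**Conclusion.** The point holds as a risk of detection bias affecting the child's report and the assessor's findings. It should be fixed. The child opening the envelope and the assessor's unrestricted access to results are the clearer conflicts. The overlap between sequence generator and assessor is real but partly protected by the random draw. The statistician's blinding is not contradicted.

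The size of any bias cannot be estimated from the documents, and none is claimed. The figures of two or three calls rest on the protocol's planning rates, one success-or-failure call per subject, all changes in one direction, and complete data at 20 or 23 per group. They show how little error would matter, not that such error is expected.

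**What to change.** **Section 16.** Have someone who neither treats nor assesses generate and hold the list. Of the three investigators in Section 5, the second author fits and can do this remotely. Keep the list, and any record of which numbered envelope a child received, from the assessor until database lock. The child may still pick an envelope, but the operator opens it out of sight of child and parent. Say also who fills and seals the envelopes, which the section does not state. If envelopes are opened in order instead, custody of the list becomes critical, because the list plus enrolment order would then reveal each arm.

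**Section 21.** Either move monitoring of results from the assessor to another team member, or limit the assessor to records without the arm and without results by arm before database lock. Reconcile this with the data-monitoring role in Section 5.

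**If these steps are not adopted,** amend Sections 8 and 17 to state who is actually blinded.

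**Cost.** One small added task for the second author, whose listed role is writing revision and proofreading, and a few sentences in Sections 5, 16 and 21. Opening the envelope out of sight leaves the operator as the only described witness. The envelope change can help only children not yet allocated, and the documents do not give the trial's status. Sample size, visits and assessments do not change. One route stays open: Section 6 names discoloration as a drawback of MTA and describes less of it with Biodentine, so a visual examiner might still guess the arm.

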Vital pulp therapy has been increasingly considered as a minimally invasive approach for the management of teeth with inflamed pulps compared to the conventional approach of root canal treatment [12,13]. Among the factors that contributed to this choice are (1) the high frequency of technically inadequate root fillings and associated apical periodontitis despite new technologies in root canal preparation and filling , (2) the numerous advantages of VPT in terms of preserving tooth structure ,maintaining possible proprioceptive defensive mechanisms of the remaining pulp, and reducing the propensity of tooth fracture, (3) comparable success rates of VPT compared to RCT over five years of follow-up [6,7] .

Traditionally Ca (OH)₂ has been used for VPT for many years [14]. Recently MTA has replaced Ca (OH)₂ due to its ability to form an apatite-like layer, its

biocompatibility and its lack of cytotoxicity [15]. MTA due to its, biocompatibility and its ability to form cementum attachment has not only been used as a root-end filling material but also has been used as in pulpotomy, apexification, direct pulp capping and as a perforation repair material but has some drawbacks like handling property, high cost, long setting time and discoloration [14].

A magical capsule to overcome the limitations of MTA raised in the dental field called (Biodentine) [15]. It is considered a calcium silicate cement that was introduced as a ‘dentine replacement’ material, comparable to MTA in terms of biocompatibility and induction of a calcific barrier [16]. It possessed additional improvement of several properties such as mixing, handling, shorter initial setting time (12 min, with reports from 6.5–45 min) and less coronal discoloration [13].

Limited clinical data were available on the use of Biodentine in VPT; recently only three clinical trials compared Biodentine to MTA as pulp capping materials for cariously exposed teeth with high success rate approaching 100% at 1-year follow-up in young patients. [16] In a case report, Biodentine was successful in pulpotomy of traumatized permanent incisors at 48 months of follow-up [17,18].

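### Blinding of families and of the clinical and radiographic assessor is claimed without qualification, although the protocol says the two materials discolour visible front teeth to different degrees and describes no masking or check

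*Combined protocol and SAP*

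**What the plan says.** Section 8 describes the trial as "Triple blinded (patient, clinical and radiographic assessor of the results and statistician". Section 17 adds the parents: "Patients and their parents, the assessor and the statistician will be blinded". Neither statement is qualified, and neither says how the blind is kept during 18 months of follow-up.

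Section 6 compares the materials. MTA "has some drawbacks like handling property, high cost, long setting time and discoloration", while the listed improvements of Biodentine include "less coronal discoloration". Section 10 admits "Unilateral/ and or bilateral central incisors tooth with complicated trauma". Under IV, Intervention, the control material is "white mineral trioxide aggregate (MTA) ProRoot".

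The clinical findings (pain, swelling, sinus tract, mobility) form the primary outcome. Root development stage and radiolucency, read on periapical radiographs, are secondary (Sections 12 and 18). Section 18 has the assessor make the postoperative records.

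**The concern.** A blind holds only if nothing the observer sees points to the arm. Here the plan's own rationale names a visible property on which the materials differ, and the study teeth are among the most visible in the mouth. The clinical examiner is a specialist in the field and one of the investigators (Sections 5 and 12), so can be expected to know the colour comparison that the protocol itself makes.

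Two things are at stake. The first is detection bias in the components that need judgement. The second is the credibility of the report, which would claim a triple blind that its own introduction calls into question, with no data to show whether the blind held.

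**Working it through.** The point disputes no figure in the plan. The check is mainly a comparison of sections, followed by the arithmetic that bears on size.

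**1. Who sees the crown, and what they supply (Sections 12 and 18)**

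| Component | Source | Exposure to a colour cue |
|---|---|---|
| Pain | Child and parent are asked | Both see the tooth daily; the cue matters only if they know which material discolours |
| Percussion/palpation sensitivity | Listed with the pain questionnaire in Section 12, not repeated in Section 18 | Who elicits it is not stated |
| Swelling, sinus tract | Assessor looks | Crown in or near view; fairly objective signs |
| Mobility | Assessor, back of the mirror | Crown in view; a yes/no judgement |
| Root stage, radiolucency | Periapical radiograph | Crown colour is not on the film, but the same visit may show it |

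Mobility is the clearest case: it needs judgement, and the person making it can be expected to know the colour difference.

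**2. Radiographs**

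For the control arm: "A 3-mm-thick layer of MTA will be placed over the amputated pulps". For the experimental arm: "radicular pulp will be covered by the material using a wet cotton pellet", with no thickness. The Biodentine thickness is unstated; it is not stated to differ. Nothing says that the two materials look different on a film. What can be established is that the images are of the treated tooth and that no coding, masking or separate reading is described.

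**3. Protection**

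Sections 12 and 17 to 21 contain no order of assessment, image masking, record of tooth colour or check of the blind.

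**4. Size of one changed result**

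The plan's group size is reproduced first. Inputs from Section 14: success 0.90 and 0.50, alpha 0.05 (taken as two-sided), power 80%. The mean proportion is 0.70.

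n = [1.96 × √(2 × 0.70 × 0.30) + 0.842 × √(0.90 × 0.10 + 0.50 × 0.50)]² / 0.40² = 19.4, rounded up to 20 per arm. Then 20 × 1.15 = 23, as stated.

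One result scored differently moves an arm's rate by 1/23 = 4.3 points with all children followed, or 1/20 = 5.0 points at the planned minimum.

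**5. Sensitivity of the comparison to misrecording (illustration only)**

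Assumptions that are not in the documents: true success is 90% in both arms, there are 20 per arm, and a share m of true successes in one arm, whichever it is, is recorded as failure. The recorded rate is q = 0.90 × (1 − m). Summing the exact binomial probabilities of all tables with two-sided p ≤ 0.05 gives the chance of a false significant result:

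| m | q | Fisher's exact | Uncorrected chi-square |
|---|---|---|---|
| 0% | 0.900 | 1.2% | 3.9% |
| 5% | 0.855 | 2.6% | 6.5% |
| 10% | 0.810 | 6.2% | 12.2% |
| 20% | 0.720 | 20.0% | 30.7% |
| 30% | 0.630 | 41.2% | 54.5% |

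Not every recognised child is misrecorded. If half of an arm were recognised and one in five of its true successes among them were miscored, m would be 0.5 × 0.2 = 10%. The table shows what a given error would do. It does not show that the error occurs.

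**The case against.** The case on the other side is substantial, and much of it stands.

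- **Colour does not identify the arm.** Section 6 makes a general comparison with no rate, timing or degree. The control is the white form of MTA, and less discolouration is not none. A discoloured crown is at most a hint. This stands, and it makes unmasking a risk of unknown frequency. It does not make the unqualified claim of blinding safe.
- **Families may not be able to read the cue.** Nothing available shows that they are told which material discolours. This stands, and the pain report is therefore only conditionally exposed.
- **The films may carry no cue.** A reader might infer from the 3 mm specification for MTA that the arms can be told apart on radiographs. The documents do not support that, because an unstated thickness is not a different one and no difference in appearance is described.
- **The direction of any bias is not known.** A reader might infer a bias towards Biodentine, since the research question asks whether it is more successful. The planning figures in Section 14 (90% for MTA, 50% for Biodentine) point the other way, so no direction should be asserted.
- **Other routes to unblinding are more direct.** The child opens the envelope, the third author both generates the sequence and examines for swelling and sinus tract, and the assessor has full access to data and results (Sections 12, 16 and 21). These are separate matters. Correcting them would leave the colour cue in place.

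**Conclusion.** The point holds as a gap between what is claimed and what is protected. The protocol acknowledges differential discolouration, treats visible incisors, claims that families and the assessor are blinded, and describes neither a safeguard nor a check.

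The size of the resulting bias cannot be estimated. A reader might want a number of recognisable control children, but with no discolouration rate it could be anything from none to all 23, and any figure in between would be invented. What can be said is that the trial is small enough for one or two judgements to matter, at 4.3 to 5 points each.

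The conclusion rests on two assumptions: that the assessor knows the colour comparison in Section 6, and that no masking procedure exists outside the protocol. The risk would be greater if two incisors in one child could receive different materials and be compared side by side. Section 16 speaks of assigning access cavities and Section 10 admits bilateral cases, but whether such teeth are assigned separately is not clear.

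**What to change.** 1. **Order of assessment.** Complete and lock the clinical score at each visit before the radiograph is viewed.
2. **Image reading.** Code the digital radiographs and read them without group labels, apart from the clinical visit. Black out the pulpotomy material and restoration where this removes no structure needed for root staging. Section 12 does not define the four stages, and the material sits at the canal orifice, so set the mask line only once the stages are defined.
3. **Record of the cue.** Add a yes/no field for visible crown discolouration at each visit, filled in after outcome scoring, and report it by arm. This shows how far colour could have revealed the allocation.
4. **Wording.** In Sections 8 and 17, say that parents and the clinical assessor are not told the allocation but may be unmasked by tooth colour.

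No step can hide crown colour from a child or parent who sees the tooth every day, which is why the claim needs rewording as well as better procedures. The cost is minor image handling, one form field and a more modest blinding claim. Treatment is unchanged, and no extra visits are needed.
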